A second cost utility analysis will also be performed. This model will also take an NHS perspective and use costs based on HES data as for the cost effectiveness model, but additionally will use outcomes based on QALY data (primary EQ5D data collected through the field work in a subgroup of SIHHC users at baseline and three month follow up). Data from the two types of service will also be compared to each other and homeless controls from a wider London based survey of 455 homeless individuals accessing Find and Treat screening service for tuberculosis. QALY loss due to morbidity and mortality averted will be examined. Cost estimates will be based on HES data and calculated at two time points: baseline, including retrospective data up to 3 month prior enrolment in the study, and follow up, including prospective data up to 3 month service follow up. Outcome data (QALY) will be calculated from EQ5D data collected at baseline and 3 month follow up.

Cost and effectiveness estimates to be calculated for one year follow up period after entering the study with simulations to 20 years and costs will be discounted at 3.5% per annum. A sensitivity analysis will be carried out in order to examine uncertainties within the cost effectiveness and utility model to examine the uncertainty within the parameters used.

A third cost utility analysis will also be performed using costs and health outcome (consented) data collected from the 6 case study sites. This model will take an NHS and also a wider public sector perspective (e.g. exploring costs for use of social care, prison, supported housing etc.).

The added value of this third economic analysis would be to estimate the cost utility of hospital discharge services from a larger public sector perspective whilst incorporating contextual information from the realist evaluation into the economic evaluation.

The objective of this economic evaluation will be to:

- Evaluate the effect of SIHHC on access to resources and their attached costs (health and mental health services, drug and alcohol services, social care services, housing situation) and on individual wellbeing, and how effect may vary across schemes in different sites
- Compare the effect of SIHHC on access to resources and individual wellbeing to sites relying on standard provision only (i.e. those that do not have access to SIHHC)
- Evaluate any variation in effect of SIHHC across time (dependent on opportunities for tracking participants over the longer term)

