Where feasible, data on access to resources will be collected up to 12-month from discharge. This will allow capturing changes in yearly estimate before and after participating in SIHHC. To determine the effect of the SIHHC we will compare individual service use and health outcome after joining the study (based on 3-month follow-up) with our estimate of their service use had they not participated (one year prior to the enrolment). The specialist schemes will then be compared to the standard schemes which will be assessed in the same way. Cost of care will be estimated multiplying individual-specific health care resource utilization by unit cost using available tariff.

Sample size for economic evaluation:

Data from our 455 controls from Find & Treat provides a mean EQ5D visual analogue scale score of 65 and standard deviation of 25. An important improvement (or worsening) in the EQ5D visual analogue scale (0 to 100) as result of the provision of specialist services to this group would be 10. Using a power of 80% at the 0.05 level of significance (two sided) and a two sample *t* means test it is estimated that a sample size of 100 is required to detect such a change. Based on our previous work it is assumed that of all eligible service users identified, 80% of these will consent to take part in the study, and therefore 126 individuals will need to be approached to achieve this sample size. Therefore, 63 individuals will be approached at each of sites 1-6 (for a total of 378 individuals).

Sensitivity analysis and economic discounting: Cost and effectiveness estimates to be calculated for one year follow up period after entering the study with simulations to 20 years and costs will be discounted at 3.5% per annum. A sensitivity analysis will be carried out in order to examine uncertainties within the cost effectiveness and utility model to examine the uncertainty within the parameters used.

Additional ethical issues

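### The third economic analysis sets three months of service use after joining against twelve months before, with no rescaling stated

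*Protocol*

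**What the plan says.** All references are to the Protocol, Health Economics Analysis, unless stated.

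**Third analysis (six case study sites, NHS and wider public sector perspective).** Three consecutive sentences matter:
- On data collection: "Where feasible, data on access to resources will be collected up to 12-month from discharge".
- On purpose: "This will allow capturing changes in yearly estimate before and after participating in SIHHC".
- On the effect itself, individual service use and health outcome are compared "after joining the study (based on 3-month follow-up) with our estimate of their service use had they not participated (one year prior to the enrolment").

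Standard-care sites are then assessed by the same method and compared with the specialist ones.

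**Second analysis.** Its costs come from HES at two points with matched windows: "baseline, including retrospective data up to 3 month prior enrolment in the study, and follow up, including prospective data up to 3 month service follow"-up. On outcomes: "Outcome data (QALY) will be calculated from EQ5D data collected at baseline and 3 month follow up".

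**Horizon.** "Cost and effectiveness estimates to be calculated for one year follow up period after entering the study with simulations to 20 years". This appears in the text on the second analysis and again under Sensitivity analysis and economic discounting, with a general sensitivity analysis of the model parameters.

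**Data sources.** The consented questionnaires are at baseline, exit and 3 months (Data sets used for WP2). Linked HES follow-up runs to November 2016 or death (Study design).

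**The concern.** The three sentences on the third analysis do not fit together. The first two aim at twelve months on each side of enrolment. The third, which defines the effect, uses three months on one side and twelve on the other. It does not say whether totals or rates are compared.

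This analysis is meant to add items that HES does not hold, such as social care, prison and supported housing. For those items the planned contacts in Appendix One, Box 2 stop at 3 months, so the 12-month data offered where feasible may often be absent. If the effect rule is followed literally, an artefact of window length enters the cost side of the cost per QALY.

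A related but separate point concerns the outcome side. The QALYs rest on EQ5D at baseline and 3 months, while the reported horizon is one year and then 20 years. How much of the one-year figure is observed depends on a course after month 3 that the Protocol does not state.

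**Working it through.** **The section's own figure.** The only computed number here is the EQ5D visual analogue sample size: difference 10, SD 25, 80% power, two-sided 5%. The two-sample formula gives 99 (99.08 with the t distribution), consistent with the stated 100, read as per group. With 80% consent, 100/0.8 = 125, and 126 = 2 x 63 gives 126 x 0.8 = 100.8. The figure reproduces and this point does not affect it.

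**1. Window length, one person.** Let use be constant at rate r per year.
- Before: 1 x r. After: 0.25 x r. Change: -0.75r, an apparent fall of 75%.
- At 0.7 episodes per person-year (borrowed from the readmission sample size, for illustration): 0.175 after against 0.70 before.

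**2. Does the comparison with standard sites cancel it?** Let rS and rC be the annual rates at specialist and standard sites, with no effect of SIHHC.
- Difference in changes = (0.25rS - rS) - (0.25rC - rC) = -0.75(rS - rC).
- This is zero only if rS = rC.

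| Assumed rates | Result with no true effect |
|---|---|
| rS = 1.1rC | -0.075rC |
| rS = 1.2rC | -0.15rC |
| rS = 0.9rC | +0.075rC |
| rS = 0.8rC | +0.15rC |
| rS = 1.0, rC = 0.7 per year | -0.225 episodes |

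**3. Does multiplying the 3-month figure by four repair it?** Only if the first three months have the same rate as the whole year. Let the early rate be f times the annual rate.
- Difference in changes = (4 x 0.25 x f - 1)(rS - rC) = (f - 1)(rS - rC).
- With f = 1.5 and rS = 1.2rC (both assumed): 0.5 x 0.2rC = +0.10rC, so the sign reverses.
- For Poisson counts the standard error of the annual rate doubles. At 0.7 per year and n = 126: sqrt(0.7/126) = 0.075 from 12 months of data, and sqrt(0.7/(126 x 0.25)) = 0.149 from 3 months.

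**4. QALY horizon.** Assume a utility difference of 0.10 that builds linearly from zero to month 3.
- Observed part: 0.5 x 0.10 x 0.25 = 0.0125.

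| Course after month 3 (assumed) | Added after month 3 | One-year gain | Share observed |
|---|---|---|---|
| Held to month 12 | 0.10 x 0.75 = 0.075 | 0.0875 | 14% |
| Linear fade to zero at month 12 | 0.5 x 0.10 x 0.75 = 0.0375 | 0.050 | 25% |
| Linear fade to zero at month 6 | 0.5 x 0.10 x 0.25 = 0.0125 | 0.025 | 50% |
| Lost at month 3 | 0 | 0.0125 | 100% |

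Between the first two rows, cost per QALY at a fixed incremental cost changes by 0.0875/0.050 = 1.75 times.

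**The case against.** The strongest reply is that the text points to a common time base. It speaks of yearly change, calls the comparator an estimate, and allows resource data to 12 months where feasible. Scaling detail is often left to an analysis plan, which is not at hand. This stands in part: annualisation may be intended. But none is written, the sentence defining the effect names two unequal windows, and step 3 shows that multiplying by four brings its own assumption. Recall periods and follow-up contacts also have to be settled before data collection, so a later plan cannot fully repair them.

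Four stronger readings are tempting, and the Protocol does not support them.
- **A reader might infer that all the economic results rest on three months of service use.** They do not. HES runs to November 2016 or death, the primary model uses HES costs and readmission outcomes, and the second analysis has equal 3-month cost windows.
- **A reader might infer a false saving for SIHHC, because inner-city specialist sites would have heavier users.** Site Selection speaks of larger homeless populations and the resources they need, not of use per person. Sites 3 and 4 are metropolitan/rural, and Sites 5 and 6 are given no location. The direction is unknown.
- **A reader might infer that the one-year QALY is an error, or that most of it must be assumed.** Extrapolation is openly modelled. The share observed depends on the course after month 3. An exit questionnaire has no fixed date, and some sites collect EQ5D on all users (Appendix One, Box 5), so later readings cannot be ruled out.
- **A reader might infer that the base case must be cut to 3 months.** That is a trade-off. The Protocol's own account of the earlier Pathway trial notes that short follow-up limits the benefit that can accrue.

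It is also fair that a 3-month window before enrolment is no cure by itself. Participants are enrolled a few days after discharge (Appendix One, Box 2), so the index admission would dominate a short window.

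**Conclusion.** The point holds for the third economic analysis only. As written, its effect rule compares 0.25 with 1 person-year without rescaling and conflicts with the aim stated in the sentence before it. The 75% apparent fall under constant use follows from the windows alone. The bias in the specialist-versus-standard contrast is -0.75 times the gap in baseline use. Its size of 7.5% to 15% of the standard sites' annual use rests on an assumed gap of 10% to 20%, and its sign cannot be read from the Protocol. With equal baseline use it vanishes.

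The QALY point is one of reporting and sensitivity. The planned EQ5D supports a 3-month result directly, while the one-year and 20-year figures depend on an unstated course after month 3. The QALY sizes assume a difference of 0.10 and linear change between time points. Neither comes from the Protocol.

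**What to change.** **Third analysis.** Reconcile the three sentences.
- Use equal windows before and after enrolment, or rates per person-time with the window named for each item.
- Use 12 against 12 months only for items where both periods are complete, such as linked HES.
- State whether the index admission falls in the period before enrolment. Either exclude it or handle it identically in specialist and standard sites.

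**QALYs.** Report the 3-month within-study result beside the one-year and 20-year figures. In the planned sensitivity analysis, include the EQ5D difference both held and fading to zero after month 3.

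**Cost.** This is mainly wording, but the recall period in the baseline questionnaire may need to change. Shorter windows hold fewer events and give less precise cost estimates. The 3-month QALY gain will be smaller than the extrapolated one wherever any benefit persists beyond month 3.

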1. **Unconsented data:** SIHHC (hospital discharge projects) taking part in the study (Sites 1-2, 7-13 using clinically led services; Sites 3-4, 14-20 using non-clinically led services) will be asked to provide identifying and demographic data (forename, surname, aliases, date of birth, sex, current or previous postcodes, nationality, ethnicity, NHS number) for service users during the period November 2013 to a maximum of November 2016. However, note that for some services we will collect data that ends before 2016 as some will have been shut down before this time period and in some we may collect data at an earlier point, providing we receive the appropriate permissions and ethical and CAG approvals.
2. **Consented data from a subset of study fieldwork sites (n=6 sites):** We will collect data on 252 individuals across 4 sites with SIHHC (hospital discharge) schemes (two sites that are clinically led (Sites 1&2), two sites that are non-clinically led (Sites 3&4)) and on 126 individuals across two sites with standard /usual care (Sites 5&6), giving 378 individuals in total (63 per site x 6 sites). The data collection for this part of the work is contained in a baseline, exit and 3-month follow up data questionnaire and will collect information on demographic information, along with dates of contact with SIHHC services, past use of health and social care services, mental health services, smoking, alcohol, and drug taking history, prison and homeless history, employment, user satisfaction with service delivery, and data on quality of life (EQ5D). The voluntary sector hospital discharge projects will be asked to help collect this data on behalf of the research team as part of their routine outcomes monitoring and will be reimbursed for doing so at a rate of £20 per completion. The data flow chart shows how this work will be integrated with WP1 for practical purposes.
3. The data flow chart shows how this work will be integrated with WP1 for practical purposes.

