Confounding variables: As this is a virtual cohort, we will not be able to collect a complete set of confounding variable data on individuals at entry to the study. Where data is provided by SIHHC services we will include age (year and month only), sex. As a result of the lack of baseline data will use historical HES data to determine past medical history from the age of 18 which will be used to create a variable to control for co-morbid conditions and historical hospital usage. Analyses will therefore control for age, gender, comorbidities (identified from HES data) and reason for admission, classified by Healthcare Resource Group (HRGs – groupings of treatment episodes which are similar in resource use and clinical response). Subgroup analyses will compare the different types of SIHCC services. Where provided by the SIHHC services, we will also control in subgroup analysis for medical symptoms, past use of health and social care services, mental health services, smoking, alcohol, and drug taking history, prison and homeless history, employment history.

Health Economics Analysis:

This analysis will cover three economic models. The primary analysis will be a cost effectiveness model (linked to effectiveness data described in the comparative effectiveness section). This model will take an NHS perspective, with costs based on the linked HES data analysis and outcomes based on morbidity and mortality data. Outcomes of homeless users of the two types of SIHHC service (clinically led and non-clinically led) will be compared to each other and homeless controls. Outcomes used for this analysis will include: 1. Overall hospital readmission rates; 2. Unscheduled readmission rates; 3. 28-day emergency readmission rates. Cost estimates will be calculated using national NHS

tariff data, and will include length of hospital stay, emergency admissions, and fixed and variable costs estimates for each of the SIHHC services.

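### QALYs built from baseline and 3-month EQ5D are compared between non-randomised site groups with no stated adjustment for baseline EQ5D, so a case-mix gap enters the incremental QALY

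*Protocol*

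**What the plan says.** **Data.** Under Data sets used for WP2, item 2 (the consented sample at Sites 1-6), the protocol says: "The data collection for this part of the work is contained in a baseline, exit and 3-month follow up data questionnaire". The questionnaire includes EQ5D. In Appendix One, Box 2, the baseline questionnaire is completed at a community visit arranged a few days after discharge, for Groups A and B alike.

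**QALY construction.** Under Health Economics Analysis, second cost utility analysis: "Outcome data (QALY) will be calculated from EQ5D data collected at baseline and 3 month follow up". The two service types are compared with each other and with homeless controls from a Find and Treat survey of 455 people. No regression model or covariate is named.

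**Covariates.** The one fixed list is under Confounding variables: "Analyses will therefore control for age, gender, comorbidities (identified from HES data) and reason for admission". It belongs to the virtual cohort built from HES and does not contain baseline EQ5D.

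**Sizing.** Sample size for economic evaluation starts from a "mean EQ5D visual analogue scale score of 65 and standard deviation of 25" and an important difference of 10 points. It continues "Using a power of 80% at the 0.05 level of significance (two sided) and a two sample *t* means test" and concludes that "it is estimated that a sample size of 100 is required to detect such a change".

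**Groups.** Sites are selected purposively, two per type. Figure 1 puts the clinically led pair in inner London and an inner city, and the non-clinical pair in metropolitan or rural areas.

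**The concern.** A two-point QALY is the area under the line joining the baseline and 3-month EQ5D index, so each value carries half the weight. In a randomised comparison a baseline gap would be chance. Here service type is tied to site, the sites are chosen to differ in setting, and participants are identified through scheme or ward discharge coordinators. A difference in health between the groups at baseline is to be expected.

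If raw QALYs are compared, that gap becomes part of the incremental QALY although it is not gained during follow-up. A service type whose sites take healthier people would look more cost-effective with no true effect. The same section then extends cost and effectiveness to 20 years by simulation, and the results may inform the commissioners' toolkit. The baseline measurement needed to deal with this is already being collected.

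**Working it through.** **Inputs.** From the protocol: SD 25, difference 10, two-sided 5%, 80% power, stated size 100, 80% consent, 63 approached per site, two EQ5D measurements 0.25 year apart. Not in the protocol, so assumed: a baseline to 3-month correlation rho of 0.3 to 0.7, equal SD at the two times, and illustrative baseline index gaps of 0.05 and 0.10.

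**1. The protocol's own figure.** n per group = 2 × (1.96 + 0.84)² × 25² / 10² = 98.0. Unrounded normal quantiles give 99 and the exact t solution is 99.1, so 100 per group. The stated 100 reproduces only as a per-group size; as a total (50 per group) power would be 51.6%. Allowing for consent, 100 / 0.8 = 125, against 126 = 2 × 63. Power at 100 per group is 80.7% (normal approximation). The sizing is sound on its own terms.

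**2. Baseline gap carried into the QALY.** QALY = 0.25 × (U0 + U3) / 2 = 0.125 × (U0 + U3). Suppose there is no true effect, a baseline gap d, and a 3-month gap of rho × d:
- directly through U0: 0.125 × d
- in all: 0.125 × d × (1 + rho)

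| d | direct | total, rho 0.3 | total, rho 0.5 | total, rho 0.7 |
|---|---|---|---|---|
| 0.05 | 0.0063 | 0.0081 | 0.0094 | 0.0106 |
| 0.10 | 0.0125 | 0.0163 | 0.0188 | 0.0213 |

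For comparison, a true gain of 0.05 present at 3 months and absent at baseline is worth 0.125 × 0.05 = 0.0063 QALY.

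**3. If the gap persists in full to 3 months.** The raw QALY difference is 0.125 × 2d = 0.0125 for d = 0.05. Adjustment removes 0.125 × (1 + rho) × d and leaves 0.125 × (1 - rho) × d, which is 0.0031 at rho 0.5. On the VAS, a persistent 5-point gap falls to 5 × (1 - 0.5) = 2.5 points. The bias is reduced but not removed.

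**4. Precision on the VAS.** Adjusted SD = 25 × sqrt(1 - rho²), with 100 per group measured at 3 months:

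| | unadjusted | rho 0.3 | rho 0.5 | rho 0.7 |
|---|---|---|---|---|
| SD | 25.0 | 23.8 | 21.7 | 17.9 |
| Power | 80.7% | 84.3% | 90.4% | 97.7% |

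**5. Precision of the QALY.** The ratio of adjusted to unadjusted variance is (1 - rho²) / (2 + 2 rho) = (1 - rho) / 2, that is 0.35, 0.25 and 0.15 at rho 0.3, 0.5 and 0.7. This cannot be turned into power for the QALY, because the protocol gives neither the SD of the index nor a target QALY difference.

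**The case against.** **The t test is not an analysis specification.** This stands. It appears only as the basis for the sample size, and the word unadjusted does not occur. A reader might infer that an unadjusted t test is the planned EQ5D analysis and that the study loses power; the protocol supports neither reading. No EQ5D analysis model is named, and the planned 80% is met. The point about QALYs does not depend on the t test.

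**Covariates for a QALY regression can be left to an analysis plan.** That is often so, and such a plan may exist. But this protocol fixes how QALYs are built and which groups are compared, and it fixes covariates for the HES cohort only. Followed as written, it gives a poorer estimate than the collected data allow.

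**Other passages describe change.** The text after the secondary outcomes will explore how quality of life changes, and the third economic analysis has a before/after step. So baseline is not wholly ignored. But the prior-year estimate in that step is of service use, not EQ5D, and neither passage governs the QALY comparison. If change scores were meant for the VAS, power would be 66.7%, 80.7% and 95.5% at rho 0.3, 0.5 and 0.7.

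**The gaps are hypothetical, and adjustment is no cure.** This stands in part. The 0.05 gap is illustrative. If site differences persist, step 3 shows that regression leaves a residue, and it does not deal with other confounding or with having only two sites per type.

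**Baseline is taken after discharge support may have begun.** This stands. If baseline already holds an early effect e, adjustment removes 0.125 × (1 + rho) × e from the QALY difference. The protocol gives no basis for calling that small.

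**Conclusion.** The concern holds for the QALY comparison. With no stated adjustment for baseline EQ5D between purposively selected groups, an index gap of 0.05 produces a spurious 0.008 to 0.011 QALY at rho 0.3 to 0.7, at least as large as the 0.0063 from a true 3-month gain of 0.05. These figures rest on the assumed correlation, a straight-line two-point QALY and an illustrative gap; the direct component of 0.0063 does not depend on the correlation.

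There is no power shortfall. Adjustment would add about 4 to 17 percentage points to VAS power over the same range of rho, which is a gain in efficiency and not a repair. A reader might also infer a specific and large loss of power for the QALY; the documents do not allow one to be calculated, since carrying over 0.4 SD (10/25) would apply a VAS effect size to an index whose SD is not given.

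This is a change that should be made. It does not invalidate the design.

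**What to change.** In Health Economics Analysis, including Sample size for economic evaluation, state that:

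- incremental QALYs will be estimated by regression on service type with baseline EQ5D index, age and sex as covariates;
- the 3-month VAS will be analysed in the same way with baseline VAS, age and sex;
- this applies where both groups have baseline and 3-month EQ5D: clinically led v non-clinical, and each v Sites 5-6;
- the two-sample t test remains the sizing basis only;
- the unadjusted QALY difference and the unadjusted 3-month EQ5D differences will be reported as sensitivity analyses, because baseline may already hold part of an early effect.

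The Find and Treat comparison is not covered: the variable list for that group (Appendix One, Box 5) shows a screening date and EQ5D but no follow-up EQ5D.

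The cost is one or two sentences of wording, with no new data, visits or participants. The price in interpretation is that the adjusted estimate may understate an effect already present a few days after discharge, and that persistent site differences are reduced but not removed.

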APPENDIX ONE: FLOW CHARTS

Box 1: Summary Table of Data to be Collected in Each Study Site

	WP1 In-depth fieldwork Topic Guides 1-6	WP2 Consented EQ5D Baseline +Follow-Up Questionnaires	WP2 Unconsented
Realist Evaluation Case Study Sites			
Site 1 – SIHHC Clinically led	✓	✓	✓
Site 2- SIHHC Clinically led	✓	✓	✓
Site 3 – SIHHC Non-clinical (e.g housing link worker)	✓	✓	✓
Site 4 – SIHHC Non-clinical (e.g. housing link worker)	✓	✓	✓
Site 5 – Usual/Standard Care	✓	✓	✓
Site 6 – Usual Standard Care	✓	✓	✓
Other Research Sites			
Site 7 – SIHHC Clinically led			✓
Site 8 – SIHHC Clinically led			✓
Site 9 – SIHHC Clinically led			✓
Site 10 – SIHHC Clinically led			✓
Site 11 – SIHHC Clinically led			✓
Site 12 – SIHHC Clinically led			✓
Site 13 – SIHHC Clinically led			✓
Site 14 – SIHHC Non-clinical (e.g housing link worker)			✓
Site 15 – SIHHC Non-clinical (e.g housing link worker)			✓
Site 16 – SIHHC Non-clinical (e.g housing link worker)			✓
Site 17 – SIHHC Non-clinical (e.g housing link worker)			✓
Site 18 – SIHHC Non-clinical (e.g housing link worker)			✓
Site 19 – SIHHC Non-clinical (e.g housing link worker)			✓
Site 20 – SIHHC Non-clinical (e.g housing link worker)			✓

Box 2: Arrangements for Data Collection in Fieldwork Sites 1-6*

Scheme Typologies Across Fieldwork Sites 1-6

Sites 1&2: In these sites the hospital has access to a specialist integrated hospital discharge scheme (SIHHC) for homeless people which is ‘clinically-led’

Sites 3&4: In these sites the hospital has access to a specialist integrated discharge scheme (SIHHC) for homeless people which is non-clinical (e.g. provides access to housing advice only)

Sites 5&6: In these sites the hospital does not have access to any specialist schemes for discharging homeless service users (i.e. ‘standard or usual care’)

Stakeholder Recruitment (n=60)

In each of these 6 sites, a minimum of 10 stakeholders (practitioners, managers and clinicians) will be recruited for semi-structured interview as part of Work Package 1 (Realist Evaluation). Prospective participants will be given an invitation letter and project information sheet. Informed consent will be ascertained prior to commencement of the interview.

Service user Recruitment (n=378)

In each of these 6 sites a total of 63 service users will be recruited:

In each site:

10 service users will be allocated to Group A

53 service users will be allocated to Group B

Group A (n=10 service users)

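### The EQ5D sample size allows for refusal of consent but not for loss by 3 months or for clustering by site, and 63 per site means approached in one section and recruited in others

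*Protocol*

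**What the plan says.** The Protocol, under *Sample size for economic evaluation*, sizes the EQ5D comparison on the visual analogue scale (VAS). Find & Treat data "provides a mean EQ5D visual analogue scale score of 65 and standard deviation of 25". The important change "as result of the provision of specialist services to this group would be 10". With a two-sample t-test, two-sided at 5%, and a target of 80% power, the section gives its result as follows: "it is estimated that a sample size of 100 is required to detect such a change". It then assumes 80% consent, raises the number to 126, and ends: "Therefore, 63 individuals will be approached at each of sites 1-6 (for a total of 378 individuals".

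Other sections use the same 63 and 378 differently:

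- *Appendix One, Box 2*: "In each of these 6 sites a total of 63 service users will be recruited", split into 10 in Group A and 53 in Group B. The Group B steps repeat 53 recruited per site (318 in all).
- *Data sets used for WP2*, consented data: data will be collected on 252 people in four specialist sites and 126 in two standard sites, "giving 378 individuals in total (63 per site x 6 sites".
- *Summary of Research*: EQ5D data are to be collected and analysed for 63 service users per site, 378 in total.

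On timing, the second cost-utility analysis under *Health Economics Analysis* states: "Outcome data (QALY) will be calculated from EQ5D data collected at baseline and 3 month follow up". The same paragraph compares the two service types with each other and with Find and Treat controls. The third analysis compares specialist with standard schemes, with the effect based on 3-month follow-up.

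**The concern.** There are two linked problems.

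First, 63 per site cannot be both the number approached and the number recruited if one person in five declines. As written, a site cannot tell when recruitment is complete.

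Second, the only inflation is for consent. Nothing is added for people who complete the baseline questionnaire but not the 3-month one, although the outcome needs both. The t-test also treats people as independent when each care type is represented by two sites. The Protocol accounts for hospital clustering in its survival models but not in this calculation.

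The problems are linked because the meaning of 63 decides whether there is any reserve for loss. At stake is whether the stated 80% power holds for the 3-month EQ5D comparisons, and whether a null result between service types could be read as informative.

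**Working it through.** **Inputs from the Protocol.** SD 25, difference 10, two-sided alpha 0.05, power 80%, two-sample t-test, consent 80%, 63 per site, two sites per care type. **Assumptions, not in the Protocol:** retention at 3 months and the intracluster correlation (ICC).

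**1. Reproducing the plan's figure.** n per group ≈ 2(1.96 + 0.84)² × 25² / 10² = 98. The exact t calculation needs 99.1, so 100 per group (power 80.4%). The Protocol does not write "per group", but 100 in total (50 per group) would give only 51% power, so per group is the reading that fits. Consent: 100 / 0.8 = 125, or 126 as an even number over two sites, i.e. 63 per site. The arithmetic is sound.

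**2. The two meanings of 63.**
- Approached: 378 × 0.8 = 302 participants; 126 × 0.8 = 100.8 per pair of sites.
- Recruited: 378 participants; 126 per pair of sites.
- Difference: 378 − 302 = 76 participants.

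**3. Reserve for loss, two sites against two sites.**
- Approached: 1 − 99.1/100.8 = 1.7%, under two people per group.
- Recruited: 1 − 99.1/126 = 21%.

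**4. Power for a 10-point difference among 3-month completers** (exact t, no clustering):

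| Retention (assumed) | Two v two sites, approached | Two v two sites, recruited | Four v two sites, approached |
|---|---|---|---|
| 100% | 81% | 89% | 90% |
| 90% | 76% | 85% | 87% |
| 80% | 71% | 81% | 83% |
| 70% | 66% | 75% | 78% |
| 60% | 59% | 69% | 71% |

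For four v two sites, 80% power needs 74.2 in the smaller group, so the tolerated loss is 1 − 74.2/100.8 = 26%.

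For two v two sites at 80% retention, the difference detectable with 80% power is 11.1 points (approached) or 9.9 points (recruited).

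**5. Clustering, for illustration only.** Two v two sites, full follow-up, design effect 1 + (m − 1) × ICC:

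| Reading | ICC | Design effect | Effective n per group | Power |
|---|---|---|---|---|
| Approached, m = 50.4 | 0.01 | 1.494 | 67.5 | 64% |
| Approached, m = 50.4 | 0.02 | 1.988 | 50.7 | 51% |
| Recruited, m = 63 | 0.01 | 1.62 | 77.8 | 70% |
| Recruited, m = 63 | 0.02 | 2.24 | 56.2 | 56% |

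A design effect alone is optimistic here. Two sites per group leave 2 degrees of freedom in a site-level analysis, and power at ICC 0.01 is then about 27% (approached) or 30% (recruited).

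**The case against.** A reader might infer that any loss at all defeats the stated power. The documents do not support that in general. It is true, beyond the 1.7% margin, only when 63 means approached and two sites are compared with two. The recruited reading absorbs about 21% loss. The Protocol also plans comparisons with more people: specialist against standard schemes (four v two sites), and each service type against 455 Find and Treat controls. For the latter, 100.8 v 455 has 95% power, and still 83% after 40% loss in the service group, ignoring clustering. The two-site contrast is the weakest, but it is planned, since the two service types are to be compared with each other.

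A reader might also infer that site clustering demonstrably breaks the power. That rests on an ICC the Protocol does not give. What stands is that the calculation ignores clustering.

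Nor does the Protocol state an expected loss for the EQ5D follow-up. Its mention of attrition concerns peer researchers keeping in touch with participants, and its replacement rule covers only the 10 key informants per site. This does not close the gap: the Group B steps, covering 53 of 63 people per site (84%), describe neither safeguard.

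Baseline adjustment could recover power (about 83% at 20% loss on the approached reading, if the baseline to 3-month correlation were 0.5). The sample-size section states no such adjustment.

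Finally, this is not the study's main sizing. The primary economic model uses linked hospital data, not EQ5D.

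**Conclusion.** The point holds in a limited form. The conflict between approached and recruited is certain, needs no assumption, and amounts to about 76 participants. The absence of any allowance for 3-month loss is also certain from the text. Its effect depends on the reading and the contrast: it matters almost at once for two v two sites if 63 are approached, beyond about 21% loss if 63 are recruited, and beyond about 26% for four v two sites if 63 are approached. Those thresholds rest on the Protocol's own SD and difference for the VAS, an unadjusted t-test and no clustering. The clustering figures show sensitivity only. The error lies in what the sample size is said to deliver, not in its arithmetic, and it concerns a secondary economic comparison. It should be corrected, but it does not threaten the readmission analysis.

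**What to change.** 1. Give 63 one meaning in the Summary, the WP2 data-set list, the economic sample-size section and Appendix One (Box 2 and the Group B steps). The sponsor should confirm whether approached or recruited was planned and budgeted.
2. Write "per group" beside the 100, and name the contrast it refers to: between the two service types, each type against standard care, or pooled specialist against standard.
3. State the expected 3-month retention. Restate power, or the detectable VAS difference, for 3-month completers over a range of retention and ICC, acknowledging two sites per care type.
4. Describe as exploratory any contrast whose restated power is well under 80%.

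**Cost.** If recruited was the intent, the changes are to text only; recruiting 63 implies approaching about 79 per site (63 / 0.8). If approached was the intent, moving to 63 recruited would add about 76 participants, with questionnaires, community visits and, where schemes collect the data, £20 per completion. In that case keep the sample and restate the power. Either way the stated power becomes less favourable.
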